6.0 Study Withdrawal/Discontinuation

Subjects may elect to withdraw from the study at any point. The investigator may discontinue an individual's participation in the study for the following reasons:

- 1) The participant becomes pregnant.
- 2) The subject is found during screening to have laboratory results, physical findings, or psychiatric history that are exclusion criteria.
- 3) The subject has an adverse events of moderate severity or greater who, in the judgment of the principle investigator, may be unable to complete the study or whose health may be compromised by further participation. If an adverse event occurs, immediate treatment will be provided.
- 4) A subject cannot complete the study in a reasonable period of time, i.e. >3 months. Subjects will be informed of this possibility orally and then in writing prior to discontinuation.

If a subject is discontinued by the investigator during the initial session of the study or because of a failed drug screen, they will not be reimbursed for their time. If they are discontinued because of medical or psychiatric reasons, they will be compensated at a rate of \$10 per hour spent in the study up to a total of \$150. If the study was discontinued after administration of [¹⁸F]fallypride, the subjects will be paid for the complete study.

7.0 Statistical Analysis Plan

Aim 1 tests the hypothesis that aspects of mesolimbic DA function are associated with age differences in decision behavior.

PET Analyses. A region of interest (ROI) approach will be used in the first set of analyses to examine age group differences in D2 binding (placebo BP_{ND}), DA release (Δ BP_{ND}), and DAT uptake in a set of eight brain areas. We will define subcortical (e.g., caudate, putamen, globus pallidus, thalamus) ROIs based on adapted methods developed for adults of various ages [173] by consultant [name]. We will define a lateral cortical ROI based on the results of a PCA (as in [153]) We will also anatomically define smaller key regions of interest in the midbrain (VTA/SN), ventral striatum (nucleus accumbens), and ventromedial prefrontal cortex using previously published guidelines [110,111] within individual subjects. For initial analyses all ROIs

will be averaged bilaterally, but follow-up tests will also be conducted to determine whether any ROIs warrant bilateral specification. D2 BP_{ND} (placebo) will be extracted for all eight ROIs, while DA release (Δ BP_{ND}) and DAT expression will be extracted from ROIs restricted to only those where there is substantial signal to noise (e.g., VTA/SN and striatal sites for DAT).

We will first test for expected age related differences in DA variables, using ANOVAs with Age group as the independent between subjects variable of interest. Separate analyses will be performed for BP_{ND}, Δ BP_{ND}, and DAT measures. We will also test for interactions between age group and region to test the hypothesis that there will be larger age differences in DA D2-like receptor availability in the pallidum and frontal cortical regions, but smaller (but measurable) declines in the ventral striatum. We expect that middle-aged adults will show significantly lower levels of DA release in the striatum and medial prefrontal cortex and DAT expression in the striatum compared to younger adults.

We will next test whether the dopaminergic measures predict behavioral differences in decision making. Across both groups, we expect individuals with greater DA release in the ventral striatum and ventromedial prefrontal cortex to be more tolerant of effort costs.

Aim 2 examines the hypothesis that individual and age-related differences in DAT are associated with dAMPH-induced DA release. This will be studied using striatal ROIs and ANOVA with age group serving as a between subjects variable.

Aim 3: To examine the influence of dAMPH-induced DA release on cost-benefit decision making in young adulthood and late middle age. We expect that tolerance of physical effort will be increased under dAMPH in both age groups, with differences in the extent of modulation correlating with measures of baseline DAT functioning and DA release. This will be accomplished by ANOVA analysis with age group as a between subjects variable.

Mediation Analyses: In each of the above cases we will utilize a mediation analysis to test whether expected age differences in behavior (effort performance, responsivity to d-AMPH) are mediated by age related differences in regional DA functions.

Exploratory voxel-wise analyses: Beyond the ROI analyses, more exploratory whole-brain voxelwise analyses will be conducted. For these analyses, individual difference measures (e.g., choice preferences, trait affect, cognitive ability, etc) and age will be mean-deviated and entered as regressors of interest to predict BP_{ND}. The resulting whole-brain maps will be thresholded at whole brain $p_{\text{cluster-corrected}} < 0.05$.

Relative Influence of Different DA Measures. By assessing multiple aspects of the DA system it will be possible to assess the relative influence of different aspects of the DA system on behavioral measures. We will first use a PCA analysis of ROI data for cortical and subcortical ROIs for binding potential, striatal and ventromedial prefrontal DA release, and striatal and midbrain DAT. We expect there to be a positive correlation between all of these variables, reflecting an overall integrity of the DA system, but for separate components to arise reflecting region and measure specific variance [153]. We will then assess the relative impact of the DA variables, by utilizing step-wise regression to determine which variables provide the strongest influence on the behavioral variable, and whether, as predicted, a combination of DA measures provides significantly greater explanation of the behavioral variable than the measures taken in isolation. Further, we expect the inclusion of each additional measure of DA function to reduce the significance of the age effect on differences in sensitivity to effort costs. We expect that a model that includes D2 receptors, DA release, and DAT expression will reduce the age effect to

non-significance, indicating that the age effects are mediated by the DA variables. We will also formally test a mediation model.

Control for Morphometry: When imaging the aging brain it is extremely important to address age differences in morphometry. Aside from common issues that arise with BOLD fMRI [108], findings from prior PET studies of aging may be limited by a lack of control for morphometric changes with age. Lacking information on morphometry, it is possible that observed declines in striatal D2 BP_{ND} could be partially due to changes in grey matter rather than a specific D2 deficit. An additional *innovation* of this project is that we will examine the role of morphometric change, by directly examining whether controlling for grey matter volume changes the results, applying partial volume averaging corrections for ROI analyses, and voxelwise procedures based on voxelwise morphometry techniques (see [154,174] for method details and feasibility).

Statistical Power: The analyses of age differences will be conducted with age as a dichotomous variable. The group difference effects that have been observed in relevant recent studies of decision making or corticostriatal brain activity [109-112] range from around $d=0.75-1.5$. To detect the lower extent of these effects, a total sample size of at least 60 (30 per group) is recommended for a power of .80 at $p < .05$ two-tailed. Across the sample and within age groups, we will examine relationships between continuous measures (e.g., task performance, cognitive ability, emotional traits, fMRI neural activity, PET DA measures). The individual difference correlations that have been observed in related studies range on average from $r=0.3-0.6$. To detect an average correlation of $r=.5$ within each age group (with up to two other covariates in the model), a sample size of at least 32 is recommended for a power of .80 at $p < .05$ two-tailed. Individual difference analyses that combine the age groups ($N=64$) will provide a power of over .95 to detect a correlation of $r = .50$ at $p < .05$ two-tailed (allowing for up to three covariates in the model). An r of this level is consistent with our past level of correlations between individual difference measures and DA BP_{ND} within healthy young samples [78,79]. We will also require this sample size to have sufficient power to detect interaction effects (see later hypotheses on age differences in DA measures).

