Based on preliminary data, we expect to observe larger age differences in DA D2-like receptor availability in the pallidum and frontal cortical regions, but smaller (but measurable) declines in the ventral striatum. We hypothesize that middle-aged adults will show significantly lower levels of DA release in the striatum and medial prefrontal cortex and DAT expression in the striatum compared to younger adults. Across both groups, we expect individuals with greater DA release in the ventral striatum and ventromedial prefrontal cortex to be more tolerant of effort costs.

Aim 2: To examine the influence of individual and age-related differences in DAT on dAMPH-induced DA release. Given that DAT is the primary site on which dAMPH acts, we will test the hypothesis that individual differences in DAT expression substantially predict DA release and the subjective effects of dAMPH. Because DAT declines with age, we additionally hypothesize that dAMPH-induced DA release will be lower in the middle aged than the young adult sample. We additionally predict that the combination of DA midbrain autoreceptor levels and striatal DAT levels will predict dAMPH induced DA release better than either index in isolation.

Aim 3: To examine the influence of dAMPH-induced DA release on cost-benefit decision making in young adulthood and late middle age.

We recently demonstrated that dAMPH increases tolerance of physical effort costs in healthy young adults. Young and middle-aged adults will complete a behavioral version of the effort-based task in two sessions (placebo, dAMPH). We expect that tolerance of physical effort will be increased under dAMPH in both age groups, with differences in the extent of modulation correlating with measures of baseline DA functioning and DA release.

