 - k) Diabetes, hypoglycemia, or any condition that could would prevent the participant from fasting for 6 hours
 - l) Recent participation in studies involving radiation or routine occupational exposure to radiation.
 - m) High blood pressure (Systolic B.P. > 150), or an abnormal EKG indicating potential cardiac risk under conditions of increased blood pressure. If subject is over 60, baseline B.P. > 145.

Inclusion/Exclusion criteria are determined based on data obtained during IRB#141812 (with the exception of the plasma pregnancy exam for women of child-bearing potential which is collected within 48 hours prior to each PET scan. At any point in the study, the study PI ([name]), or one of the study physicians may withdraw a participant if they find new evidence that the participant has an exclusionary condition.

Up to 70 subjects may be consented for the study, with the aim of having 60 subjects total complete the PET studies. No more than 60 subjects (30 per age group, with equal gender representation). No subjects will be consented after the 60th participant is scheduled for a PET scan unless we have another withdrawal from the study.

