4.44 Post administration blood draws. 4 blood draws (3 ml each) are taken to measure plasma amphetamine levels. These are collected at 30, 60, 90, and 175 minutes post-amphetamine. In order to avoid a different blood draw schedule, blood draws will additionally be made on the placebo day and will be discarded using appropriate hazardous biospecimen procedures. The lab will receive a sealed form that indicates whether to analyze or discard the samples.

4.45 PET scanning and fallypride administration. Scanning will be accomplished with a GE Discovery STE PET/CT scanner. 5 mCi of [¹⁸F]fallypride (specific activity > 3,000 Ci/mmol) will

be injected, and subjects will be scanned for 3.5 hours (with two 15 minute breaks) to allow estimates of both striatal and extrastriatal binding potential. Dots are placed on the subject's forehead and cheeks for periodic visual checks of alignment throughout the scan period, and for repositioning after breaks. Three CT scans will also be collected during each session for attenuation correction. Blood pressure will be taken during each break and mood ratings will be taken during each break. During the second break participants will be given a high fat meal to help improve elimination of the radioisotope. Participants will also be given fluids to drink and asked to void their bladder.

At the conclusion of each PET scan on drug and placebo day, vital signs-blood pressure, pulse, temperature and respirations – will be measured, a brief motor neurological examination performed, and an additional 3.5 ml of blood drawn for a CBC and a comprehensive metabolic panel (CMP). If neurological exam and vital signs are normal the participants will be released from the study. In the unlikely event that they are not normal, the participant will be asked to stay under medical supervision in the VUMC (in one of the rooms in the PET center) until these measures have normalized. At the time of release participants will be given instructions to drink fluids and void their bladder at least once every two hours for up to 6 hours after the time of the start of the PET session.

4.5 *FE-PE2I PET Session*

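### The age-by-region interaction on BP_ND has no stated scale and no planned contrast, so it can reflect regional signal level rather than where the age decline is larger

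*Combined protocol and SAP*

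**What the plan says.** Section 2.0, Aim 1, states the regional hypothesis: "we expect to observe larger age differences in DA D2-like receptor availability in the pallidum and frontal cortical regions", with smaller but still measurable declines in the ventral striatum. It rests on preliminary data that are not shown.

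Section 7.0, PET Analyses, extracts placebo D2 BP_ND from eight ROIs, compares age groups by ANOVA, and adds the regional test: "We will also test for interactions between age group and region to test the hypothesis that there will be larger age differences" in pallidum and frontal regions than in ventral striatum. It mentions no log transform, percentage difference, within-region standardisation, planned contrast or sphericity correction. The morphometry paragraph adds grey-matter and partial-volume control, which does not settle the scale.

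On size, Section 3.2 caps the study: "No more than 60 subjects (30 per age group, with equal gender representation". Under Statistical Power the age-group effects "range from around $d=0.75-1.5", and for the lower end "a total sample size of at least 60 (30 per group) is recommended for a power of .80". For interactions there is only an assertion: "We will also require this sample size to have sufficient power to detect interaction effects". No interaction effect size, SD, correlation or scale is given.

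**The concern.** BP_ND is a ratio-scale quantity. An age-by-region interaction on untransformed values compares BP_ND units lost in one region with units lost in another, and units lost equal the regional level times the fractional decline. A region with a high level can therefore lose more units while declining by a smaller percentage. If the hypothesis is about proportional decline, the named test then answers a different question, and its sign can depend on regional level alone.

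A second weakness holds on any scale. An omnibus interaction over eight regions asks whether the age difference varies anywhere among them. The hypothesis is directional and concerns particular regions: pallidum and frontal cortex against ventral striatum. A significant omnibus result could come from the thalamus or caudate.

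At stake is the interpretation of Aim 1's regional claim. With the scale open, it could also be chosen after the data are seen.

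**Working it through.** **The plan's own figure.** For d = 0.75, power .80 and alpha .05 ("at $p < .05$ two-tailed"), the noncentral t calculation gives 29 per group; 30 per group gives power 0.815. The stated 60 reproduces. It concerns the simple group difference, so it neither supports nor refutes this point.

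**Inputs.** From the documents: 30 per group and two-sided .05. Assumed, because the documents are silent: between-subject CV 15% in each region, inter-region correlation 0.5, lognormal BP_ND, and the level ratio R = ventral striatum / frontal.

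**Algebra.** Let the young frontal mean be m and the young ventral striatal mean Rm, with fractional declines p (frontal) and q (ventral striatum).

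- Untransformed contrast: pm − qRm = m(p − qR). It is zero at R = p/q and changes sign beyond it. For p = 15% and q = 5% that is R = 3.
- Equal declines, p = q: mp(1 − R), which is non-zero for every R other than 1.
- Log contrast: ln[(1 − q)/(1 − p)], which is free of R and is zero when p = q.

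**Hand check, 15% against 5%.**

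- Log scale: the contrast is ln(0.95/0.85) = 0.111. The log SD is √ln(1 + 0.15²) = 0.149. With correlation 0.5 the within-person difference has SD 0.149 × √(2 × 0.5) = 0.149. So d = 0.111/0.149 = 0.75, and power at 30 per group is 0.81.
- Untransformed, R = 2, m = 1: the contrast is 0.15 − 0.10 = 0.05. Variance of the within-person difference in the young is 0.15² + 0.30² − 2(0.5)(0.15)(0.30) = 0.0675. In the older group it is 0.1275² + 0.285² − 2(0.5)(0.1275)(0.285) = 0.0612. The pooled SD is about 0.254, so d = 0.05/0.254 = 0.20 and power is about 11%.

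**Simulation, two regions, t test on the within-person difference.** A dash means not tabulated.

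| R | 15% vs 5%: significant as predicted, untransformed | same, log | uniform 10% decline: significant, untransformed | same, log |
|---|---|---|---|---|
| 0.5 | 98% | 81% | 33% (mirror image of R=2) | 5% |
| 1 | 76% | 81% | 5% | 5% |
| 1.5 | 32% | 81% | 17% | 5% |
| 2 | 11% | 81% | 33% | 5% |
| 3 | 2.6% | 81% | – | 5% |
| 10 | 0.2% | 81% | 72% | 5% |

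At R = 10 the untransformed test is significant in the opposite direction in about 15–16% of trials. At R = 0.5 it favours the hypothesis, including in the uniform-decline case where the percentage declines do not differ.

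**Eight regions.** With a uniform 10% decline, CV 15% and correlation 0.6, the untransformed omnibus F is significant in 40% of trials (34% with Greenhouse-Geisser) at a two-fold spread of levels, and in 87% (77%) at ten-fold. On log BP_ND it is about 5%. The sphericity correction does not remove the scale effect.

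**Sensitivity of the log figure.** At R = 10, raising the frontal CV to 25%, 30% or 40% lowers log-scale power from 81% to about 50%, 39% and 24%. With correlation 0 it is 52%.

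**The case against.** Four points on the other side deserve weight.

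1. *Regional levels.* A reader might infer that the regions have very different binding levels and that the test will therefore fail. The documents do not support this. They report no regional BP_ND; Section 4.45 says only that the scan is long enough "to allow estimates of both striatal and extrastriatal binding potential". Section 7.0 limits DA release and DAT to ROIs with adequate signal to noise, which suggests regional signal differs for those measures but gives no ratio for D2 BP_ND. At R = 1 the two scales perform nearly alike (76% against 81%). This stands, and it is why the result is shown over a range.

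2. *Meaning of larger.* A reader might infer that the untransformed test is simply wrong. Neither section says percent. If absolute BP_ND differences are meant, the untransformed interaction is the matching test. This stands too: the defect is an undefined scale on which the answer depends. That the ANOVA is untransformed is itself the natural reading of a silent text.

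3. *Direction, especially for the pallidum.* The working covers frontal cortex against ventral striatum. For the pallidum the level ratio is equally unknown, and a higher pallidal level would make the test too favourable. No single direction of bias can be claimed.

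4. *Sphericity.* A reader might infer that the omnibus test has inflated type I error. The plan does not rule out a correction, so this cannot be charged as an error.

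The interaction is also an added step within Aim 1; it does not set the sample size, and the data can be re-expressed at analysis. That lowers the severity. It does not remove the case for fixing the scale and contrast in advance.

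**Conclusion.** The concern holds as a should-fix, with moderate confidence. As written, the regional test has no declared scale and no contrast matching its directional hypothesis. If BP_ND is analysed untransformed, modest differences in level matter: at R = 1.5 power for a 15% against 5% decline falls from 76% to 32%, and at R = 2 one uniform-decline trial in three yields a significant two-region interaction.

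The algebra needs no assumptions beyond the level ratio. The percentages depend on the assumed CV, correlation, declines and R, none of which the documents give. The log-scale power of 81% is not guaranteed; larger regional CVs or weaker correlation reduce it.

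**What to change.** Amend Section 7.0, PET Analyses, as follows:

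- State that larger means larger in proportion, and make log(BP_ND) the scale for the regional comparison, with the untransformed analysis as sensitivity. If the sponsor does mean absolute units, say so and give the reason.
- Replace reliance on the omnibus interaction with two pre-specified contrasts in log age difference: pallidum minus ventral striatum, and frontal minus ventral striatum. Name the ROIs that count as frontal, and say whether both contrasts must succeed.
- For any omnibus test, use Greenhouse-Geisser or an unstructured covariance.
- Report regional age differences as percentages with 95% confidence intervals.
- Under Statistical Power, give the interaction effect size, scale, CV and correlation behind the claim of sufficient power.

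The cost is SAP wording only, with no added participants, scans or visits. The downsides are that results are reported as ratios, and that near-zero or negative BP_ND needs a handling rule stated in advance.

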In Part I of this study we are examining behavioral and neural sensitivity to monetary reward and physical effort costs in young adulthood and late middle age. In a sample of healthy young (ages 20–30) and late middle-aged (ages 50–60) adults, we are using functional MRI to examine basic aspects of reward processing using the Monetary Incentive Delay (MID) task and sensitivity to effort costs using the Effort Expenditures for Reward Task (EEfRT). Participants in Part I of the study are also screened for eligibility for Part II of the study.

In the present (Part II) portion of the study, we will use positron emission tomography (PET) imaging to determine whether individual differences in DA functions are related to the decision-making and fMRI measures collected in Part I of the study. DA imaging will include striatal and extrastriatal baseline D2 receptor availability, amphetamine-induced DA release (a marker of DA system responsivity) and DA transporter levels. This approach provides a more comprehensive evaluation of DA functions than in prior studies attempting to link individual differences in dopamine to behavioral, cognitive or decision-making functions. In addition to allowing us to test key hypotheses about DA and behavior, this study will also allow us to address several questions about age-related and individual differences in DA functions, including 1) whether age related declines in striatal and extrastriatal D2 receptor levels covary with changes in DAT, 2) whether there are age related changes in DA system reactivity to amphetamine, and 3)

whether individual differences in baseline levels of DAT uptake are associated with the amount of amphetamine-induced DA release (which is predicted given that DAT is the target site for amphetamine, but has never been tested in humans. Additionally, we will be able to examine whether baseline differences in DAT are related to the behavioral effects of amphetamine

2.0 Specific Aims:

There are three specific aims of this phase of the study

Aim 1: To test the hypothesis that multiple aspects of mesolimbic DA function are uniquely associated with age differences in decision behavior.

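### The age-group ANOVA assigned to Aim 2 has no DAT term and so cannot test whether DAT predicts dopamine release, and the autoreceptor-plus-DAT hypothesis has no model or decision rule

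*Combined protocol and SAP*

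**What the plan says.** Section 2.0, Aim 2, sets out three hypotheses about dopamine release:

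1. "individual differences in DAT expression substantially predict DA release and the subjective effects of dAMPH".
2. "we additionally hypothesize that dAMPH-induced DA release will be lower in the middle aged than the young adult sample".
3. "the combination of DA midbrain autoreceptor levels and striatal DAT levels will predict dAMPH induced DA release better than either index in isolation".

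The first is presented as new. Section 1.0 says the link is predicted "given that DAT is the target site for amphetamine, but has never been tested in humans".

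In section 7.0 the Aim 2 paragraph has two sentences. The first gives the hypothesis that "individual and age-related differences in DAT are associated with dAMPH-induced DA release". The second gives the method: "This will be studied using striatal ROIs and ANOVA with age group serving as a between subjects variable". The paragraph mentions no DAT covariate, regression, correlation, midbrain region or subjective-effect rating.

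Four other parts of section 7.0 bear on the point:

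- **PET Analyses (Aim 1)** plans separate age-group ANOVAs for D2 binding, release and DAT. Placebo D2 binding "will be extracted for all eight ROIs", and these include the VTA/SN; DAT is taken from the VTA/SN and striatal sites.
- **Mediation Analyses** begins "In each of the above cases we will utilize a mediation analysis to test whether expected age differences in behavior", so its outcome is behaviour.
- **Relative Influence of Different DA Measures** plans a step-wise regression asking whether several dopamine measures together explain more than each alone. The outcome is again behavioural.
- **Statistical Power** says relationships among continuous measures, PET dopamine measures included, will be examined both in the whole sample and inside each age group. It allows up to two covariates within a group and three in the combined sample.

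**The concern.** The Aim 2 paragraph hands a question about a continuous predictor to a model that contains only age group. A significant result would show that release differs by age. It would say nothing about whether people with more DAT release more dopamine, which is the novel claim.

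An analyst who notices this must choose a DAT–release analysis unaided: pooled, age-adjusted or within group. These answer different questions. The choice matters here because the protocol expects both DAT and release to fall with age, and two measures that each fall with age correlate in a pooled sample even with no link between them inside either group.

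The third hypothesis is in a similar position. Its predictors, outcome and comparison are stated in advance, but nothing says which models are compared or what result would count as better than either alone.

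**Working it through.** **Inputs.** Section 7.0, Statistical Power: 30 per group, two-sided 5%, group differences of d = 0.75–1.5, correlations of r = 0.3–0.6. Those effect sizes come from related studies. The documents give none for release, so d and r below are assumptions. Simulations use unit within-group SD and 20,000 trials per setting.

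**Step 1. The plan's own figure.** For a two-group comparison at d = 0.75 with 30 per group, the noncentrality is d × √(n/2) = 0.75 × √15 = 2.905 on 58 df. Power is 0.815 (0.828 by normal approximation), and 29 per group is the smallest size reaching 0.80 by t test. The stated 30 per group is sound.

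**Step 2. What that ANOVA says about DAT.** Its noncentrality depends only on d and n. Simulated rejection confirms this, against the DAT term in a model of release on DAT and age group (both measures shifted by 0.75):

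| Within-group DAT–release r | Age-group ANOVA on release | DAT term, adjusted for age group |
|---|---|---|
| 0 | 82% | 5% |
| 0.3 | 82% | 65% |
| 0.4 | 82% | 89% |
| 0.5 | 82% | 98% |

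With no age gap in release the ANOVA rejects 5% of the time, even at r = 0.5. Fisher's z supports the last column: with 60 people and one covariate, atanh(0.3) × √(60 − 3 − 1) = 0.3095 × 7.483 = 2.316, and Φ(2.316 − 1.96) = 0.64.

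**Step 3. The general correlation plan.** A correlation computed inside each age group is free of the age-group difference. A pooled one that omits age is not. With no within-group link and both measures shifted by d, the pooled correlation is (d²/4) / (1 + d²/4):

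| d | Induced pooled r | Fisher z, 60 people | Simulated rejection |
|---|---|---|---|
| 0.75 | 0.1406 / 1.1406 = 0.123 | 15% | 15% |
| 1.0 | 0.25 / 1.25 = 0.200 | 33% | 35% |
| 1.5 | 0.5625 / 1.5625 = 0.360 | 81% | 85% |

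**Step 4. The combination hypothesis.** Setting the candidate analyses beside hypothesis 3:

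| Analysis in section 7.0 | Outcome | Compares joint with single predictors? |
|---|---|---|
| Aim 2 ANOVA | Release | No; age group only, striatal regions only |
| Mediation | Behaviour | No |
| Step-wise regression | Behaviour | Yes |
| General correlations | Any continuous measure | No |

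None has release as the outcome together with a joint-versus-single comparison.

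**Step 5. Can the sample support a test of hypothesis 3?** In a model of release on age group, DAT and midbrain D2, require both added coefficients to be significant. With standardised coefficients of size 0.3 and uncorrelated predictors, each partial r is 0.3 / √(1 − 0.09) = 0.314. Fisher's z with two covariates gives 0.3255 × √55 = 2.414, so each has power Φ(0.454) = 0.675, and both together about 0.675² = 0.46. Simulation at predictor correlations 0, 0.3 and 0.5 gives 48%, 43% and 31% when the coefficients share a sign, and 47%, 43% and 35% when the autoreceptor coefficient is negative. At 0.4 and 0.4 the range is 67–90%.

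**The case against.** The strongest reply is that the Aim 2 method sentence points back to the DAT–release hypothesis, so an analysis is assigned and merely abbreviated. Because the Aim 1 paragraph already has an age ANOVA on release, reading DAT into the Aim 2 model is the only way to keep it from being redundant. That reading is reasonable, but it supplies a term the plan does not write and leaves its form open. The need to state DAT's role stands.

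Three stronger readings are tempting, and the documents do not support them:

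- **That the age hypothesis is itself at risk.** A reader might argue that once DAT enters the model, the age term no longer tests lower release in middle age. True of that model, but the unadjusted ANOVA on release under Aim 1 already tests the age hypothesis, and nothing says an adjusted term would replace it.
- **That no DAT–release analysis exists, or that any such correlation is confounded by age.** The Statistical Power paragraph could cover the pair, and its within-group correlations avoid the age-group difference. The inflation in Step 3 applies only to the pooled version, and only if age is not among the covariates allowed.
- **That hypothesis 3 is wholly post hoc.** Section 2.0 fixes its predictors, outcome and comparison. What is missing is the model and the decision rule.

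**Conclusion.** The point holds in this limited form and should be fixed. The stated Aim 2 method duplicates an Aim 1 test and, as written, carries no information on whether DAT predicts release: about 82% rejection at d = 0.75 whatever the correlation. A general statement elsewhere may cover the DAT–release pair, but it is not tied to Aim 2 and leaves open a pooled version that would be significant 15%, 35% or 85% of the time at d = 0.75, 1.0 or 1.5 with no within-group link. Those figures assume that DAT and release shift equally with age and that age is omitted. The absence of a model and decision rule for hypothesis 3 rests on the text alone. The sample-size arithmetic for the age comparison is not in question.

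**What to change.** Leave the age comparison of release to the unadjusted ANOVA under Aim 1. In the Aim 2 paragraph, replace the ANOVA with the following:

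- **DAT and release.** Regress striatal release on striatal DAT and age group, with the DAT-by-age-group term as a follow-up. Name one striatal region, or one composite, and use it for both measures. Fit the same model to a named amphetamine subjective-effect rating, since hypothesis 1 covers that too.
- **Combination.** Add VTA/SN D2 binding. Test the R-squared change against age plus DAT, and against age plus midbrain D2. Claim better than either only if both changes are significant.
- **Interpretation.** State that the age-adjusted DAT coefficient tests the within-group, individual-difference link, and that parallel age-group declines in DAT and release do not by themselves show an association.

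The cost is wording and one to three degrees of freedom; section 7.0 already extracts the regional measures, and section 4.4 already collects the ratings. Power is the main downside: about 65% for the DAT term at r = 0.3, and about 31–48% for the both-significant rule at coefficients of size 0.3. A non-significant result on hypothesis 3 should therefore not be read as evidence against it.
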